17.1 List of Abbreviations

AE	Adverse Event/Adverse Experience
CFR	Code of Federal Regulations
CIB	Clinical Investigator's Brochure
CRF	Case Report Form
CRO	Contract Research Organization
FDA	Food and Drug Administration
GCP	Good Clinical Practice
HIPAA	Health Insurance Portability and Accountability Act
IB	Investigator's Brochure
ICF	Informed Consent Form
ICH	International Conference on Harmonization
IDE	Investigational Device Exemption
IEC	Independent Ethics Committee
IRB	Institutional Review Board
MedDRA ©	Medical Dictionary for Regulatory Activities
MOP	Manual of Procedures
NIH	National Institutes of Health
OHRP	Office for Human Research Protections
OHSR	Office for Human Subjects Research
PHI	Protected Health Information
PI	Principal Investigator
QA	Quality Assurance
QC	Quality Control
SAE	Serious Adverse Event/Serious Adverse Experience
SOP	Standard Operating Procedure
UADE	Unanticipated Adverse Device Effect
USADE	Unanticipated Serious Adverse Device Effect

1. INTRODUCTION

1.1. Background

This document describes the data analysis specifications for protocol CR-5638 titled “Long-term Evaluation of [REDACTED] UV Blocker”. The test article is the J JVCI Investigational Contact Lens [REDACTED] while the control is ACUVUE® OASYS®. This study is 2- Phase randomized, 8-visit, partially subject-masked (Control arm only), 14-week dispensing trial. The study lenses will be worn as daily wear (DW) for a period of 12 weeks, with follow-up visits occurring after 1-, 2-, 4-, 8- and 12-weeks. All visits up to visit 6 are considered to be Phase I of the study while visits 7 and 8 are considered to be Phase II of the study. After the 12-week follow-up has occurred (Phase I has completed); the habitual lenses will be worn for a period of two weeks with weekly visits (Phase II).

The document is intended to describe the guidance for statistical analysis up to the 12-week follow up (Phase 1) and will supersede section 9 in the protocol if there are any discrepancies (i.e. See Amendment History section)

1.2. Study Objectives

The primary objective of this long-term study is to evaluate the safety and efficacy the investigational contact lens [REDACTED] by comparison with ACUVUE® OASYS® both worn as daily wear modality for a period of 2 weeks.

1.3. Study Design

This is a randomized partially-masked, controlled, two arm parallel group, multi-site, 3-month dispensing study, with follow-up visits at 1-, 2-, 4-, 8- and 12-weeks of a J JVCI Investigational Contact Lens compared to Marketed Acuvue Oasys® Contact Lens. After the completion of the 12-week follow-up evaluation subjects will wear their habitual lenses for another 2 weeks, with weekly visits. Approximately 120 subjects will be screened and enrolled to ensure that at least 100 subjects complete the study.

The study begins with an initial visit (Visit 1 - Day 0). If a subject is found to meet all eligibility criteria, they will be randomized and fit with either Test or Control lens in both eyes; otherwise, the subject will be deemed ineligible for this study.

If the subject is dispensed study lenses at the initial visit, seven follow-up visits will be conducted. The follow-up visits will occur after the initial visit approximately at 1-, 2-, 4-, 8- and 12-weeks for the study lenses and 13- and 14-weeks for the habitual lenses. Unscheduled follow-up visits may occur during the study. Subjects will be advised to wear the study lenses at least 6 hours a day, for minimum of 5 days per week. On the day of the scheduled follow-up visit subjects are advised to wear the study lenses to the follow-up visits. Both the Test and Control lenses will be worn as a daily wear with lens replacement every two weeks including at the 2-, 4-, 8-week follow-up visits. Damaged or lost lenses may be replaced throughout the study.

Subjects enrolled must be at least 18 years of age at the time of consent, and habitual wearers of frequent replacement silicone hydrogel soft contact lenses in both eyes worn as daily wear.

1.4. Statistical Hypotheses for Study Objectives

This is a feasibility study and all the following hypotheses are exploratory in nature. Further analysis may be considered at the discretion of the Study Responsible Clinician.

1.4.1. Primary Hypotheses:

Efficacy

- The Test lens [REDACTED] will be significantly lower than the Control lens (ACUVUE® OASYS®), with respect to Eyestrain caused by glare score. The assessments will be made at the 2-, 4-, 8- and 12-week follow-up visits.
- The Test lens [REDACTED] will be statistically no different than the Control lens (ACUVUE® OASYS®) with respect to distance monocular LogMAR visual acuity. The assessments will be made at the 2-, 4-, 8- and 12-week follow-up visits.

Safety

- The Test lens [REDACTED] will be statistically no different than the Control lens (ACUVUE® OASYS®) with respect to percentage of eyes with grade 3 or higher slit lamp findings (Biomicroscopy). The assessments will be made at each follow-up visit.

1.4.2. Secondary Hypotheses:

Efficacy

- The Test lens [REDACTED] will be statistically no different than the Control lens (ACUVUE® OASYS®) with respect to average wearing time. The assessments will be made at the 2-, 4-, 8- and 12-week follow-up visits.

Safety

- The Test lens [REDACTED] will be statistically no different than the Control lens (ACUVUE® OASYS®) with respect to the percentage of reported symptoms, problems or complaints (yes/no). The assessments will be made at each follow-up visit.

1.5. Sample Size Justification

The plan is to enroll 60 eligible subjects per arm with a target completion of 50 subjects per arm. This is a feasibility study and the sample size was not based on any empirical calculation. A statistical power analysis is provided below for different scenarios of size effects.

The power analysis was based on historical data from 3 double masked randomized 2x2 Crossover bilateral multi-site studies [REDACTED] and [REDACTED]. Since this study is a 2-arm parallel study only data from the first period was used from each of the historical studies in the summary below. There is not a historical study available with the same design and lenses, therefore [REDACTED] and [REDACTED] were chosen since both studies contain the Test lens [REDACTED]. The study [REDACTED] was chosen since it contains the Control lens ACUVUE® OASYS®. In all three studies lenses were worn as a daily wear for approximately 2-weeks each. The follow-up visits occurred approximately at 1- and 2-weeks after the

initial visit. Out of 89 subjects enrolled in [REDACTED] 84 (94.4%) completed the study, 4 (4.5%) discontinued and 1 (1.1%) was enrolled but not dispensed (screen failure). Similarly, out of 71 subjects enrolled in [REDACTED] 67 (94.4%) subjects completed the study, and 2 (2.8%) discontinued and 2(2.8%) was enrolled but not dispensed. Lastly, out of 109 subjects enrolled in [REDACTED] 100 (91.7%) completed the study, 6 (5.5%) subjects were discontinued and 3 (2.8%) subjects were enrolled not dispensed. Of all 263 subjects who were dispensed in the studies, 185 (70.3%) were female and 78 (29.7%) were male. The ages of subjects ranged from 18 to 40 years with an average age of 29 years. Table 1 summarizes the primary endpoints data pooled from the three studies for the first period only.

Table 1: Summary of the primary endpoints data pooled from [REDACTED] and [REDACTED] Period 1 Only

SLF Grade 2	Visits			
	1-Week		2-Week	
	Test	Control	Test	Control
Corneal Edema	0(0.0)	0(0.0)	0(0.0)	0(0.0)
Conjunctival Injection	1(0.6)	0(0.0)	1(0.6)	0(0.0)
Tarsal Abnormalities	2(1.2)	11(10.7)	4(2.6)	9(9.0)
Corneal Neovascularization	0(0.0)	18(17.6)	0(0.0)	14(14.0)
Corneal Staining	0(0.0)	1(0.5)	0(0.0)	0(0.0)
Other Findings	0(0.0)	0(0.0)	0(0.0)	0(0.0)
Total Eyes (N)	154	102	150	100
Any SL Grade 2 ^b	3(1.9)	30(29.4)	5(3.3)	23(23.0)
Any SLF Grade 3+	0(0.0)	0(0.0)	0(0.0)	0(0.0)
Total Unique Eyes	154	102	150	100
Total Unique Subjects	77	51	75	50

% = nx100/N; SD = Standard Deviation

a SLF reported during an unscheduled visit were included in the following scheduled visit.

b The percent (%) of Any SLF Grade 2 is calculated using Total Unique Eyes as a denominator.

Primary Safety Endpoint (Slit Lamp Findings):

The power was estimated from the formula given by Diggle et al. (2002)² for clustered binary data for a pre-specified sample size of N=50 per arm:

$$Z_{\beta} = \frac{\left[\sqrt{\frac{N \cdot \{n(p_1 - p_2)^2\}}{1 + (n-1) \cdot \rho}} - Z_{\alpha} \sqrt{2\bar{p}\bar{q}} \right]}{\sqrt{(p_1 q_1 + p_2 q_2)}}$$

where p_1 : Response proportion in group 1 (Test), $q_1 = 1 - p_1$, p_2 : Response proportion in group 2 (Control), $q_2 = 1 - p_2$, $\bar{p} = (p_1 + p_2)/2$, $\bar{q} = 1 - \bar{p}$, n : number of observations per cluster(n was set to 10; 2 eyes x 5 time points), N is the number of subjects per arm and ρ is the common correlation across the n observations. The term z_{α} is the z score that correspond to the pre-specified type I error error α . The term z_{β} is the z score that corresponds to the estimated power $1 - \beta$ for pre-specified size effects.

There were no SLF of grade 3 or 4 reported in any of the three studies. Using previous research in the *literature*^{4,5}, the anticipated proportion of eyes with any SLF grade 3 and 4 is estimated to be less than or equal to 0.5% in both test and control arms.

Table 2: Power calculation for various effect sizes and correlations for SLF

Test Proportion	Control Proportion	Delta	Rho	Power
0.001	0.0510	.005	0.25	33%
0.001	0.0510	.005	0.50	58%
0.001	0.0510	.005	0.75	71%
0.0025	0.0525	.005	0.25	36%
0.0025	0.0525	.005	0.50	61%
0.0025	0.0525	.005	0.75	73%
0.005	0.0550	.005	0.25	40%
0.005	0.0550	.005	0.50	64%
0.005	0.0550	.005	0.75	75%
0.01	0.0600	.005	0.25	48%
0.01	0.0600	.005	0.50	69%
0.01	0.0600	.005	0.75	78%

Primary Efficacy Endpoint (Visual Acuity):

The power calculations were performed using Diggle's formula (*Diggle et al.*; 2002)² for clustered continuous data for a pre-specified sample size of N=50 per arm:

$$Z_{\beta} = \sqrt{0.5 * \left(\frac{N(n[\frac{\mu_1 - \mu_2}{\sigma^2}]^2)}{1 + (n-1)\rho} \right)} - Z_{\alpha}$$

Where σ^2 is the assumed common variance in the two groups, $\mu_1 - \mu_2$: the difference in means between the two groups (Test - Control), n : number of observations per cluster, N is the number of subjects per arm and ρ is the common correlation across the n observations.

The plan is to enroll 60 eligible subjects per arm with a target completion of 50 subjects per arm. During the enrollment period, the subject dropout rate will be closely monitored, if unexpectedly high dropout rate is observed in certain arm(s), the targeted total enrollment number will be increased accordingly in order to ensure a minimum of 50 subjects per group to complete the 3-month follow-up. Below is a table of power calculations for different effect sizes and correlations.

Table 3: Power calculation for various effect sizes and correlations for LogMAR Visual Acuity

Rho	Effect Size	Power
0.10	0.10	95.1%
0.25		95.4%
0.50		96.0%
0.75		96.3%
0.10	0.25	74.0%
0.25		77.2%
0.50		81.1%
0.75		84.0%
0.10	0.50	14.8%
0.25		20.1%
0.50		28.8%
0.75		36.5%

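### SAP Table 2 gives power for grade 3+ slit lamp findings only with Control at 5.1-6.0%, 10 to 12 times the rate the SAP anticipates, and omits the anticipated scenario

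*SAP*

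**What the plan says.** SAP 1.5, under the primary safety endpoint, first reports the historical evidence: "There were no SLF of grade 3 or 4 reported in any of the three studies". Table 1 agrees, with zero grade 3+ findings in both lens groups at both visits. From the literature the SAP then anticipates a proportion that "is estimated to be less than or equal to 0.5% in both test and control arms".

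Table 2 follows, titled "Power calculation for various effect sizes and correlations for SLF". It uses a formula "for clustered binary data for a pre-specified sample size of N=50 per arm", with the cluster size given as "n was set to 10; 2 eyes x 5 time points". Its columns are Test proportion, Control proportion, Delta, Rho and Power. The first row reads "0.001 0.0510 .005 0.25 33" (per cent) and the last "0.01 0.0600 .005 0.75 78" (per cent). Control is 0.0510, 0.0525, 0.0550 or 0.0600; Test is 0.001, 0.0025, 0.005 or 0.01; Delta is .005 throughout. Alpha is described only as "the z score that correspond to the pre-specified type I error error", without a number in this section.

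Elsewhere, SAP 6.1.1 sets a two-sided 5% level, and SAP 6.2.2 adds a 99% interval for the adjusted estimate. SAP 1.4.1 and protocol 4.1.3 state the safety hypothesis as no statistical difference between lenses in grade 3+ findings. Protocol 9.2 refers the reader to the SAP for the power analysis.

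**The concern.** For a binary endpoint, the two proportions fix both the effect and the variance, so power at 5-6% says little about power at 0.5%. No row of Table 2 keeps Control at or below the anticipated rate, and the last three rows also put Test above it, at 1%. The table has no row for the scenario described just above it.

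The safety hypothesis is one of no difference, with no margin stated, and the planned analysis is a test for a difference. How a non-significant result may be read therefore depends on what the test could have detected. A reader who takes 33-78% as the power at the expected rates would give a non-significant grade 3+ comparison more weight than it can bear.

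The Delta column adds to the problem. A reader could suppose that the table covers a half-point difference, when its proportions differ by five points.

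**Working it through.** **Inputs (SAP 1.5).** N = 50 subjects per arm; n = 10 observations per subject; rho = 0.25, 0.50, 0.75. The design factor 1 + 9·rho is 3.25, 5.50, 7.75. Alpha is not given there, so I used two-sided 5% (z = 1.960) and two-sided 1% (z = 2.576) from SAP 6.1.1 and 6.2.2, and also tried one-sided values.

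**Formula (as printed).** z_beta = [√(N·n·(p1−p2)² / (1+(n−1)rho)) − z_alpha·√(2·p̄·q̄)] / √(p1q1 + p2q2); power = Φ(z_beta).

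**1. Reproducing the first cell (0.001 v 0.051, rho 0.25, printed 33%).**
- First term: √(500 × 0.0025 / 3.25) = 0.620.
- With p̄ = 0.026, √(2 × 0.026 × 0.974) = 0.2250.
- Denominator: √(0.000999 + 0.048399) = 0.2223.
- z_alpha = 1.960: (0.620 − 0.441)/0.2223 = 0.81, power 79%.
- z_alpha = 2.326 (one-sided 1%): (0.620 − 0.524)/0.2223 = 0.435, power 66.8%, so 1 − power = 33.2%.

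Only the last value matches. Over all 12 cells, 1 − power at z = 2.326 with the 0.05 difference gives the following.

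| Test v Control | Printed "Power", rho 0.25/0.50/0.75 | 1 − power, z = 2.326 | Power, two-sided 5% |
|---|---|---|---|
| 0.1% v 5.1% | 33/58/71 | 33.2/58.3/70.8 | 79/56/43 |
| 0.25% v 5.25% | 36/61/73 | 36.0/60.6/72.5 | 77/54/41 |
| 0.5% v 5.5% | 40/64/75 | 40.2/63.8/74.8 | 73/51/38 |
| 1% v 6% | 48/69/78 | 47.6/69.0/78.5 | 67/45/34 |

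All 12 agree to about half a percentage point. No choice of 5% or 1%, one- or two-sided, reproduces the column as power. The printed column also rises with rho, whereas the design factor makes power fall. So the 5-6% Control rates entered the calculation and are not a slipped decimal; the column is type II error, at an alpha the SAP does not plan.

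**2. How far the rows are from the anticipated rate.** Control against 0.5%: 0.051/0.005 = 10.2 up to 0.060/0.005 = 12. Control against Test: 51-, 21-, 11- and 6-fold.

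**3. Same formula at smaller contrasts.** Worked example, 0% v 0.5%, rho 0.25, two-sided 5%: (√(500 × 0.000025 / 3.25) − 1.960 × √(2 × 0.0025 × 0.9975)) / √0.004975 = (0.0620 − 0.1384)/0.0705 = −1.08, power 13.9%.

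| Contrast | Power %, two-sided 5%, rho 0.25/0.50/0.75 | Power %, two-sided 1% |
|---|---|---|
| 0.1% v 0.6% (printed Delta) | 11.2/8.2/6.9 | 3.3/2.2/1.8 |
| 0.25% v 0.75% (printed Delta) | 9.0/6.9/6.0 | 2.5/1.8/1.5 |
| 0.5% v 1.0% (printed Delta) | 7.3/5.8/5.1 | 1.9/1.4/1.2 |
| 1.0% v 1.5% (printed Delta) | 5.9/4.9/4.4 | 1.5/1.2/1.0 |
| 0% v 0.5% (largest contrast within the anticipated range) | 13.9/9.9/8.2 | 4.5/2.9/2.2 |
| 0.1% v 0.5% | 9.4/7.1/6.1 | 2.6/1.9/1.5 |

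At rho 0.10, a value SAP Table 3 uses, 0% v 0.5% gives about 21% at two-sided 5%; at rho 0 it gives 35%.

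**4. Detectable difference.** With one arm at 0.5%, 80% power at two-sided 5% needs about 6.2%, 9.5% and 12.6% in the other arm for rho 0.25, 0.50 and 0.75. At two-sided 1% it needs about 8.6%, 13.2% and 17.5%.

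**5. Reliability.** At 0.5%, the expected count is 100 eyes × 0.005 = 0.5 per arm per visit, or 500 × 0.005 = 2.5 eye-visits per arm over the five visits. A normal approximation is poor there, so the figures in step 3 show order of magnitude only.

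**The case against.** The best defence is that a power table is evaluated at an alternative, not at the expected values. SAP 1.5 offers the table for a range of effect sizes, and an anticipated rate is not an upper bound. That stands: using a rate above 0.5% in one arm is legitimate, and the 80% power scenario in step 4 does the same.

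The formula is also symmetric in the two arms. Nine of the 12 rows have one arm at 0.1%, 0.25% or 0.5%, so with the labels exchanged they describe a worse Test lens. At 0.5% v 5.5% the formula gives 38-73% power at two-sided 5%.

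A reader might therefore go too far in three ways:
- **That the SAP rules out rates above 0.5%, or that the design has almost no power.** The documents say only that 0.5% or less is anticipated. Power is low for contrasts of about half a point, not for every contrast.
- **That non-significance is almost certain whatever the truth.** The 14% ceiling holds for rho of 0.25 or more; with low correlation it is 21% or higher.
- **That the sample size is wrong.** SAP 1.5 and protocol 9.2 say it was not derived from a calculation. SAP 1.4 and protocol 3.1 call the hypotheses exploratory.

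The SAP also foresaw sparse events: section 6.2.2 falls back to grade 2 or higher. That changes the endpoint analysed but does not make a grade 3+ comparison informative. No text claims that Table 2 shows adequate power.

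What the defence does not explain is why every scenario uses the same five-point gap with Control as the worse arm, why none matches the anticipated rates, and why Delta says .005.

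**Conclusion.** The point holds as an inconsistency within SAP 1.5. The text anticipates at most 0.5% in both arms, the Delta column says .005, and the calculation used a 0.05 difference with Control at 5.1-6.0%. The printed column is not power even for those inputs. Read correctly at two-sided 5%, power is about 34-79% at the tabulated rates, 4-11% at the printed Delta, and at most 8-14% with both arms within the anticipated range, for rho 0.25-0.75.

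This assumes that the SAP's formula applies, that 50 subjects per arm contribute 10 observations each, and that 0.5% is a rate per eye-visit. The SAP states it per proportion of eyes without giving the period. If it means per eye over the whole study, the per-visit rate and the power are lower. The unstated alpha does not alter the conclusion.

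The consequence is limited to how a non-significant grade 3+ result may be read. Enrolment and conduct are unaffected. It should be corrected because this is the only power statement for a primary safety endpoint.

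**What to change.** In SAP 1.5, keep N and recompute Table 2 as follows:
- Report power, not type II error, at the planned levels: two-sided 5%, and two-sided 1% for the adjusted interval. State the alpha.
- Make Delta equal to the difference of the printed proportions.
- Set Control at or below 0.5% (for example 0.1%, 0.25%, 0.5%), with Test as the higher arm, and include rows at a .005 difference.
- Add one row per rho, labelled as a detectable-difference scenario, with the Test rate giving 80% power against a 0.5% Control: about 6%, 9.5% and 13% for rho 0.25, 0.50 and 0.75 at two-sided 5%.
- Note that the low-rate values are approximate, and say whether 0.5% is per eye or per eye-visit.

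Then add two statements. First, at the anticipated rates, a non-significant grade 3+ comparison does not by itself support a conclusion of no difference in grade 3+ findings, including where the grade 2+ fallback is used. Second, grade 3+ counts will be reported per arm, with exact confidence limits on the number of subjects with any such finding. The subject is the right unit because exact limits on eyes or eye-visits would ignore the clustering.

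The cost is one recomputed table, a few sentences and one simple summary. No extra subjects or data are needed. The stated power at the anticipated rates will look much less favourable.

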5. EFFICACY

5.1. Analysis Specifications

5.1.1. Level of Significance

All planned analysis for this study will be conducted with a two-sided type I error rate of 5% for primary and secondary hypotheses. Adjustment for multiple comparisons across time will be performed using Bonferroni's method. Both adjusted and unadjusted results will be reported.

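### Both SAP power tables print the type II error as power, and Table 2 labels a difference of 0.05 as .005

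*SAP*

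**What the plan says.** SAP section 1.5 gives one clustered-data power formula for slit lamp findings and one for acuity, each "for a pre-specified sample size of N=50 per arm". In the slit lamp formula "n was set to 10; 2 eyes x 5 time points". In the acuity formula n is defined ("n : number of observations per cluster, N is the number of subjects per arm") but given no value. The quantity each formula returns, z_beta, "is the z score that corresponds to the estimated power", that is, 1 minus beta. No alpha is stated for either table.

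The results are in "Table 2: Power calculation for various effect sizes and correlations for SLF", with values from 33% to 78%, and in "Table 3: Power calculation for various effect sizes and correlations for LogMAR Visual Acuity", with values from 14.8% to 96.3%. Every Table 2 row shows Delta as .005. Just above that table, the rate of grade 3 or 4 findings "is estimated to be less than or equal to 0.5% in both test and control arms".

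On testing, SAP section 5.1.1 states: "All planned analysis for this study will be conducted with a two-sided type I error rate of 5% for primary and secondary hypotheses". Sections 5.2.2 and 6.2.2 set the Bonferroni-adjusted level at 0.01 for acuity (0.05/5) and use 99% simultaneous intervals for slit lamp findings. Protocol section 9.2 leaves the power analysis to the SAP.

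**The concern.** The tables run the wrong way. In both formulas the treatment difference is in the numerator and 1 + (n − 1)·rho is in the denominator. Power must therefore rise with effect size and, at a fixed effect, fall with rho. Table 3 falls with effect size: at rho 0.10 it prints 95.1%, 74.0% and 14.8% for effect sizes 0.10, 0.25 and 0.50. Both tables rise with rho: the first three rows of Table 2 print 33%, 58% and 71%.

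The Delta column of Table 2 also disagrees with the proportions beside it, and those proportions disagree with the anticipated rate.

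This matters because the acuity and slit lamp hypotheses are that Test and Control do not differ statistically. A non-significant result will be read as support, and its weight depends on power. As printed, Table 3 says the smallest acuity difference would be found about 95% of the time.

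**Working it through.** **Inputs.** N = 50 per arm (SAP 1.5). For slit lamp findings, n = 10 (stated). For acuity, n is not stated; n = 2 (two eyes at one visit) is inferred because it fits. Alpha is not stated; z = 2.326 (one-sided 0.01) is inferred because it fits both tables. Effect size in Table 3 is read as the mean difference divided by sigma. The formula as it appears in the text available for this review divides by sigma squared, which would not give a standardised effect.

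**Formulas.**

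- Slit lamp: z_beta = [√(N·n·(p1 − p2)² / (1 + (n − 1)·rho)) − z_alpha·√(2·p̄·q̄)] / √(p1·q1 + p2·q2)
- Acuity: z_beta = √(0.5·N·n·d² / (1 + (n − 1)·rho)) − z_alpha
- Power = Φ(z_beta); beta = 1 − Φ(z_beta)

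**Reproducing Table 3** (rho 0.10).

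- d = 0.50: √(0.5 × 50 × 2 × 0.25 / 1.10) = 3.371. Then z_beta = 3.371 − 2.326 = 1.045, so power is 85.2% and beta 14.8%. Printed as power: 14.8%.
- d = 0.10: √(0.5 × 50 × 2 × 0.01 / 1.10) = 0.674. Then z_beta = −1.652, so power is 4.9% and beta 95.1%. Printed as power: 95.1%.

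**Reproducing Table 2**, first row (0.001 vs 0.0510, rho 0.25).

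- √(50 × 10 × 0.05² / 3.25) = 0.6202
- √(2 × 0.026 × 0.974) = 0.2251
- √(0.001 × 0.999 + 0.051 × 0.949) = 0.2223
- z_beta = (0.6202 − 2.326 × 0.2251) / 0.2223 = 0.435, so power is 66.8% and beta 33.2%. Printed as power: 33%.

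Read as beta, all 12 rows of Table 2 match within about 0.5 points and all 12 rows of Table 3 within about 0.1 points. Read as power, no combination tried fits. The search covered several one- and two-sided alphas, n from 1 or 2 up to 10, and, for Table 3, N from 50 to 120. The best fit still missed its worst row by about 36 points in Table 2 and 82 points in Table 3.

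**Corrected power for acuity (%)**, rho 0.10 / 0.25 / 0.50 / 0.75, n = 2:

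| Effect size | Printed | One-sided 0.01 | Two-sided 0.01 | Two-sided 0.05 |
|---|---|---|---|---|
| 0.10 | 95.1 / 95.4 / 96.0 / 96.3 | 4.9 / 4.5 / 4.0 / 3.7 | 2.9 / 2.6 / 2.3 / 2.1 | 9.9 / 9.2 / 8.3 / 7.7 |
| 0.25 | 74.0 / 77.2 / 81.1 / 84.0 | 26.1 / 22.8 / 18.9 / 16.1 | 18.7 / 16.0 / 12.9 / 10.8 | 39.2 / 35.2 / 30.3 / 26.6 |
| 0.50 | 14.8 / 20.1 / 28.8 / 36.5 | 85.2 / 79.8 / 71.2 / 63.5 | 78.7 / 72.1 / 62.2 / 53.9 | 92.1 / 88.5 / 82.3 / 76.2 |

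**Corrected power for slit lamp findings (%)**, rho 0.25 / 0.50 / 0.75, n = 10, at the printed proportions:

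| Test vs Control | Printed | One-sided 0.01 | Two-sided 0.01 | Two-sided 0.05 |
|---|---|---|---|---|
| 0.001 vs 0.0510 | 33 / 58 / 71 | 66.8 / 41.7 / 29.2 | 57.2 / 32.2 / 21.1 | 79.0 / 56.4 / 43.0 |
| 0.0025 vs 0.0525 | 36 / 61 / 73 | 64.0 / 39.4 / 27.5 | 54.3 / 30.1 / 19.8 | 76.7 / 54.1 / 41.1 |
| 0.005 vs 0.0550 | 40 / 64 / 75 | 59.8 / 36.2 / 25.2 | 49.8 / 27.2 / 17.9 | 73.2 / 50.7 / 38.3 |
| 0.01 vs 0.0600 | 48 / 69 / 78 | 52.4 / 31.0 / 21.5 | 42.4 / 22.7 / 14.9 | 66.6 / 45.0 / 33.8 |

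**Delta.** 0.0510 − 0.001, 0.0525 − 0.0025, 0.0550 − 0.005 and 0.0600 − 0.01 all equal 0.05, ten times the printed .005. The printed values were computed from 0.05: at a difference of .005 and the same z, beta would be 94.4-98.1%, which matches no row. The Control rates of 5.1-6.0% are also at least ten times the anticipated maximum of 0.5%. With a real difference of .005 from the same Test rates, power is 1.0-3.3% at two-sided 0.01 and 4.4-11.2% at two-sided 0.05. These last figures are rough, because a 0.5% rate means about 50 × 10 × 0.005 = 2.5 events per arm and the normal approximation is poor there.

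**The case against.** The strongest reply is that nothing depends on these tables. The study is a feasibility trial with exploratory hypotheses, SAP 1.5 says the sample size did not come from a calculation, and the enrolment trigger is 50 completers per group. The inversion in Table 3 is easy to spot. Results will be reported with confidence intervals, which show the precision achieved whatever the tables say. All of this is true and limits the consequences: no analysis and no enrolment figure changes. It does not make the stated power right. Protocol 9.2 points the reader to these tables, and no other statement of detectable effects exists.

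Three narrower points stand as caveats.

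- Alpha and the acuity n are inferred from fit. The reversed direction and the Delta mismatch need neither.
- For slit lamp findings, n = 10 pools five visits, while 0.01 is a correction across visits. With n = 2 at a single visit and two-sided 0.01, the first three rows give about 28%, 22% and 18%. The two-sided 0.01 figures above therefore follow the SAP's set-up but are not the only defensible ones.
- The documents do not show whether the Delta label or the Control proportions are the slip. The arithmetic used 0.05, but .005 is closer to the anticipated rates.

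The columns cannot be rescued as the chance of correctly finding no difference. The SAP defines z_beta by power, both captions say power, and no equivalence margin is given.

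**Conclusion.** The concern holds. Both tables report beta under the heading of power, so the stated power is wrong for acuity (co-primary efficacy) and slit lamp findings (primary safety). The third primary endpoint, eyestrain, has no power table.

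Exchanging beta for 1 minus beta is not a full correction, because the fitted z of 2.326 is one-sided 0.01, whereas the planned tests are two-sided (z = 2.576 at 0.01). At the planned levels, 50 per arm has little power for an acuity effect of 0.25 SD or less (at most 18.7% at 0.01 and 39.2% at 0.05) and moderate to good power at 0.50 SD. It has almost none for a .005 difference in grade 3 or higher findings. A non-significant result for such differences would be weak evidence that the lenses are alike.

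The sizes rest on the SAP's own formulas, N = 50, n = 2 for acuity and n = 10 for slit lamp findings.

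**What to change.** - Replace both power columns with 1 minus beta at two-sided 0.05 and at the Bonferroni level, and state the alpha used.
- State the n behind Table 3 (2, if the inference is right), and check that the acuity formula divides by sigma.
- Reconcile Delta with the proportions in Table 2. If the printed proportions stay, Delta is 0.05; if .005 was meant, change the proportions and recompute.
- In either case add rows at the anticipated rates (at most 0.5%).
- Add a sentence saying that 50 per arm has little power for acuity effects of 0.25 SD or less, or for grade 3 or higher findings at the anticipated rates.

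The cost is two tables and a few sentences in the SAP, best made before results are interpreted. Enrolment and the endpoint analyses do not change. The stated power becomes less favourable for small effects and more favourable for the 0.50 acuity effect.
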